#### **Exploratory endpoints**

*12. Infectivity to mosquitoes, defined as the percentage of infected mosquitoes, in relation to gametocyte density and plasma drug levels of AQ and DEAQ (across arms assessment) [during and shortly after SMC rounds 2-4].*

The association between proportion of infected mosquitoes and gametocyte density will be determined using generalized linear models assuming a binomial distribution with a log-link for participants with and without detectable AQ/DEAQ plasma concentrations. In addition, infectivity will be compared between individuals with/without AQ/DEAQ plasma levels using a previously published statistical model (ix). In case of low infectivity, the nonparametric van Elteren's test, an extension of the Wilcoxon rank sum test that compares groups in a stratified manner will be used (iii) where we compare infectivity between groups after stratifying in gametocyte density categories. Infectivity is then compared within different bins to test for differences between arms, accounting for gametocyte density. Additional analyses will take into consideration AQ/DEAQ concentrations at continuous scale (rather than simple detectability).

*13. Size and age-distribution of the infectious reservoir for malaria, defined as the likelihood that a mosquito becomes infected with malaria parasites after feeding on a population member (between arm comparison) [during the study].*

The size and shape of the infectious reservoir will be estimated using a combination of directly observed mosquito infection events and imputed transmissibility (i, ii). This imputed transmissibility will use gametocyte density (measured for all relevant timepoints) as starting point. The association between proportion of infected mosquitoes and gametocyte density will be determined using generalized linear models assuming a binomial distribution with a log-link. If drug levels do not influence infectivity (see 8), a

single modelled association will be used. If drug levels do have a statistically significant impact on transmission potential, all estimates of the infectious reservoir within one month of SMC will take study arm into account. For the infectious reservoir at the final end of study survey, no impact of SMC drugs on transmission efficiency is assumed. The contribution of different age groups (younger than 5 years, 5–15 years, 16 years and older) to the infectious reservoir will be estimated using all data (including parasite-negative observations where zero transmission is assumed)

14. *Prevalence of drug resistance markers in infected children aged 3 months-9 years assessed post each round of SMC (between arm comparison) [during the entire study].*
15. *Description of perceived social barriers to SMC uptake [during the entire study].*
16. *Quantification of SMC efficacy decay under programmatic conditions [during the entire study].*

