For assessments of the human infectious reservoir, the intervention study is too large in scope (i.e. 558 compounds, compared to 180 in the previous INDIE project) and the time-window for transmission assays is too narrow (i.e. transmission assays are ideally done within weeks after SCM administration) to assess a direct impact of SMC on gametocyte infectivity with a conventionally powered comparison between arms. Thus a combination of methodologies (quantification of the association between gametocyte density and infectivity in the absence of treatment; imputed mosquito transmission from gametocyte density) are used (i, ii) It was further shown that direct comparisons of the association between gametocyte density and mosquito infection rates in mosquito feeding assays can demonstrate whether imputation is indeed acceptable across populations (i) or whether there are subpopulations with a different association (for example due to gametocyte-sterilizing effects of antimalarials (iii)). These insights will be used to perform mosquito feeding assays on gametocyte positive individuals with and without prior SMC and compare mosquito infection rates for a given gametocyte density (iii). Since the hypothesis is that SPAQ will permanently sterilize gametocytes, any reduced infectivity of gametocytes will remain apparent even after drug levels have waned (i.e. the gametocytes are permanently damaged by drug exposure) (iv). A possible sterilizing effect of SPAQ can be assessed by preferentially recruiting children who are gametocyte positive at the start of SMC and invite them for mosquito feeding post SMC. This will be done in children aged 5-9 years only who carry the highest parasite densities and highest gametocyte prevalence/density (i); this also avoids phlebotomy from the youngest children. A median gametocyte density of ~14 gametocytes/ $\mu$ L (IQR 1.8-44.2) as previously observed post-SMC (v, vi) is anticipated. Whilst the exact number of experiments that can be conducted will be dictated by mosquito husbandry, simulations indicate that when recruiting 100 children who received SPAQ (arm 3) and 100 children who did not (arms 1 & 2) and dissecting 40 mosquitoes per experiment, we would have >90% power to detect a 70% reduction in infectivity (vii).

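### The mosquito-infectivity GLM for exploratory endpoints 12 and 13 makes no allowance for variation between children, and the SAP leaves open both the test that decides the endpoint 13 model and the main exposure contrast

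*SAP*

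**What the plan says.** **Design.** SAP Section 7 plans mosquito feeding on "100 children who received SPAQ (arm 3) and 100 children who did not (arms 1 & 2) and dissecting 40 mosquitoes per experiment", and claims more than 90% power for a 70% reduction in infectivity. The contrast there is receipt of SPAQ. The reason given is that the drug sterilises gametocytes permanently, so that "any reduced infectivity of gametocytes will remain apparent even after drug levels have waned".

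**Endpoint 12 (Section 10.7).** The outcome is "Infectivity to mosquitoes, defined as the percentage of infected mosquitoes, in relation to gametocyte density" and drug levels. Three analyses are listed:
- "generalized linear models assuming a binomial distribution with a log-link for participants with and without detectable AQ/DEAQ plasma concentrations";
- a comparison of children with and without drug in plasma, using a published model (reference ix);
- if infectivity is low, a van Elteren test stratified by gametocyte density. Only this step mentions a comparison between arms.

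Drug concentration on a continuous scale is added as a further analysis.

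**Endpoint 13 (Section 10.7).** The same type of binomial log-link GLM supplies the imputed infectivity. If drug levels do not influence infectivity, a single association is used. If they have a statistically significant effect, reservoir estimates within one month of SMC take study arm into account. No test is named for this decision. The cross-reference goes to item 8, which is gametocyte prevalence.

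**Clustering elsewhere.** Section 10.7 names a random intercept for cluster under endpoint 1 and a random effect for compound under endpoint 11. Nothing comparable is named for endpoints 12 and 13.

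**The concern.** The child is the experimental unit: one blood sample feeds about 40 mosquitoes. Two children with the same gametocyte density can still differ in how infectious they are, and every mosquito fed on the same child shares that difference. A plain binomial GLM has no place for it. Given density, it treats 200 × 40 = 8,000 mosquitoes as independent, so its standard errors and intervals are too narrow.

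Two loose ends make this matter more. The endpoint 13 rule depends on statistical significance without naming the test, so a test with too high an error rate could be the one that decides. The exposure definition also shifts. If the effect outlasts the drug, as Section 7 assumes, then grouping by detectable AQ/DEAQ can place treated children whose levels have fallen among the unexposed. Section 2.3 schedules transmission sampling on the first day of rounds 2 to 4, about a month after the previous round, so some waning is plausible. What is at stake is the drug-effect inference in endpoint 12 and the form of the imputation in endpoint 13, which serves study objective iii.

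**Working it through.** **Inputs from the SAP (Section 7).** 100 versus 100 children; 40 mosquitoes per child; 70% reduction; power above 90%; gametocyte density median about 14/µL with IQR 1.8 to 44.2. If density is log-normal, the log SD is (ln 44.2 − ln 1.8)/1.349 = 2.37.

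**Assumed, because the SAP gives no value.** Control-group infectivity, the ICC within a child given density, and a two-sided 5% level for this endpoint.

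**Step 1: the stated power.** It cannot be reproduced exactly without control infectivity and between-child variance. With effective mosquitoes per group = 100 × 40/(1 + 39 × ICC) and a two-proportion test:
- 10% control infectivity against 3%: power 1.00 at ICC 0.1, 0.99 at 0.2, 0.95 at 0.3, 0.88 at 0.4.
- 5% against 1.5%: power 0.98 at ICC 0.1, 0.85 at 0.2.

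The claim of more than 90% is therefore compatible with many values and is not disputed.

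**Step 2: error rate of a group test from the plain GLM.** The design effect is DE = 1 + 39 × ICC. Standard errors are too small by √DE, and type I error = 2 × [1 − Φ(1.96/√DE)]. For ICC 0.05: DE = 1 + 39 × 0.05 = 2.95, √DE = 1.72, 1.96/1.72 = 1.14, type I error 25%.

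| Assumed ICC | DE | SE too small by | Type I error, formula | Type I error, simulated |
|---|---|---|---|---|
| 0 | 1.00 | 1.0 | 5.0% | 5.6% |
| 0.01 | 1.39 | 1.2 | 9.6% | not run |
| 0.02 | 1.78 | 1.3 | 14.2% | 15.8% |
| 0.05 | 2.95 | 1.7 | 25.4% | 25.7% |
| 0.10 | 4.90 | 2.2 | 37.6% | 36.8% |
| 0.20 | 8.80 | 3.0 | 50.9% | 50.7% |

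The simulation used 2,000 trials per setting, no drug effect, the density distribution above, beta-binomial counts, and 8% infectivity at median density. The log-link GLM had log density and drug group as covariates.

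**Step 3: sensitivity.**
- At ICC 0.05, 30 or 50 children per group give 25.1% and 25.7%.
- At ICC 0.10, infectivity of 3% or 15% at median density gives 37.9% and 38.6%.
- With a logit link, ICC 0.05 gives 25.8% and ICC 0.10 gives 36.9%. The link is not the cause.

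**Step 4: does a correction work?** With quasi-binomial or child-robust standard errors in the same log-link GLM, simulated type I error is 4.8% to 6.6% over ICC 0 to 0.3.

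**Step 5: the log link as a separate point.** A log link has no upper bound at 1. With an assumed 10% infectivity at median density, the fitted value exceeds 1 when log density is more than ln(10)/slope above the median. That is about 0.1%, 2.6% and 8% of the density distribution for assumed slopes of 0.3, 0.5 and 0.7. The problem is negligible for a shallow curve and visible only for a steep one.

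**The case against.** A reader might infer that this GLM is the test that steers endpoint 13, and that the steering test therefore rejects far too often. The SAP does not say so. The GLM sentence describes an association with density for participants with and without drug; it does not itself define a group test. The between-group comparison is stated in the next sentence and uses the published model. Reference ix is not at hand, so its treatment of between-child variation cannot be judged. A van Elteren test on each child's infection rate would not be inflated, although the SAP does not state its unit. This objection stands. What remains is that the deciding test is not named and its pointer is wrong.

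The size rests on an assumed ICC. That also stands, and the figures are a range, not an estimate. Only an ICC near zero would remove the problem, and the SAP gives no basis for assuming one.

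Overdispersion affects standard errors, not the fitted mean, so it does not in itself bias the imputed curve. A false-positive decision would only make the estimates within one month of SMC take study arm into account. The end-of-study reservoir is exempt. This stands and limits the consequence.

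The exposure definition could be read as a flat contradiction of Section 7. That goes too far. Section 5.3 defines endpoint 12 in relation to drug levels, the van Elteren step mentions arms, and continuous concentrations are added. No detection limit or misclassification rate is given. The smaller point survives: the powered contrast is not clearly the main one.

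**Conclusion.** The concern holds in limited form. As written, the GLM for endpoints 12 and 13 has plain binomial variance and ignores variation between children at the same density, although the SAP names random effects for endpoints 1 and 11. Its standard errors are too small by √(1 + 39 × ICC), or by 1.3 to 2.2 for assumed ICCs of 0.02 to 0.10. A drug-group test taken from it would then reject a true null about 14% to 38% of the time. These figures assume 40 mosquitoes per child, a two-sided 5% level and an ICC that the SAP does not give.

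Two specification gaps are plain from the text: the endpoint 13 decision names no test and refers to the wrong item, and the main exposure contrast in endpoint 12 differs from the one powered in Section 7.

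The documents do not support saying that an inflated test will decide endpoint 13, that the log link causes the inflation, or that the imputed reservoir is biased by overdispersion. No primary or secondary comparison is affected. Severity is low to moderate.

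**What to change.** 1. In endpoints 12 and 13, replace the plain binomial GLM with a beta-binomial model, or with a binomial model that has a random intercept for each child (feed) or quasi-binomial or child-robust variance. Use log gametocyte density as covariate. The last two variance options are the ones checked above.
2. As a minor extra, use a logit link so that imputed probabilities stay below 1.
3. Make SPAQ receipt (arm 3 versus arms 1 and 2), as powered in Section 7, the main contrast. Keep detectable and continuous AQ/DEAQ as supporting analyses.
4. Name the one test, with the child as unit, that decides between a single association and estimates that take study arm into account. State the child as unit for the van Elteren test as well.
5. Correct the cross-reference in endpoint 13 from item 8 to endpoint 12.

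The cost is a few sentences in the SAP and standard models in Stata or R, which the SAP already names. Intervals will be wider, by the factors in the table if the assumed ICCs apply.

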- iv) sampling for drug metabolite assessment shortly after the last SMC round (sample collection in all compounds in the study arms and outside-study control area).
- v) sampling for transmission assay on first day of SMC round 2 to 4 (sampling in all compounds; selection from individuals aged 5-9 years).
- vi) passive case detection in all four health facilities that are accessed by the study population throughout the study period (from enrolment until the end of follow-up).

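### Endpoint 12's model-based analyses group feeders by AQ/DEAQ detectability, but the sterilisation hypothesis and the stated power concern SPAQ receipt; the receipt contrast should be added

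*SAP*

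**What the plan says.** **Hypothesis and design (Section 7).** The SAP reasons: "Since the hypothesis is that SPAQ will permanently sterilize gametocytes, any reduced infectivity of gametocytes will remain apparent even after drug levels have waned". It plans to "perform mosquito feeding assays on gametocyte positive individuals with and without prior SMC", comparing mosquito infection rates at equal gametocyte density in children aged 5-9. The simulated power rests on "recruiting 100 children who received SPAQ (arm 3) and 100 children who did not (arms 1 & 2"), and the claim is that, "dissecting 40 mosquitoes per experiment, we would have >90% power to detect a 70% reduction in infectivity".

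**Analysis (Section 10.7, endpoint 12).** The binomial model of infection rate on gametocyte density is fitted "for participants with and without detectable AQ/DEAQ plasma concentrations". Next, "infectivity will be compared between individuals with/without AQ/DEAQ plasma levels using a previously published statistical model". A further analysis uses concentration as a continuous variable. If infectivity is low, a van Elteren test stratified by gametocyte density is used. That sentence speaks first of groups and then of arms, without saying which groups are meant.

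**Timing.** Section 2.3 lists "sampling for transmission assay on first day of SMC round 2 to 4", with rounds about 30 days apart. Section 7 and the endpoint 12 title also foresee feeds after, or shortly after, SMC.

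**Downstream rule (Section 10.7, endpoint 13).** One infectivity curve serves everyone unless drug levels significantly affect infectivity. If they do, reservoir estimates within a month of SMC allow for study arm. The rule's cross-reference is to item 8, which is gametocyte prevalence; endpoint 12 appears to be meant.

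**The concern.** Under permanent sterilisation, what matters is whether the gametocytes met the drug, not whether drug is still measurable at the feed. An arm 3 child who was dosed, whose gametocytes were damaged and whose drug has cleared belongs with the exposed under the hypothesis. Both model-based analyses put that child with the unexposed. The estimated reduction is pulled towards zero, the exposed group shrinks, and the stated power no longer describes the comparison being made.

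The result is then used in endpoint 13. There the trigger is drug level while the correction is by arm. If the trigger is diluted it may miss a real effect, a single curve would be applied, and arm 3's contribution to the reservoir within a month of SMC would be overstated. That bears on study objective iii.

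**Working it through.** **1. The planned power.** The >90% cannot be reproduced exactly, because the SAP gives neither the comparator infection rate nor the between-child variation. It was approximated by simulation: beta-binomial data, 100 versus 100 children, 40 mosquitoes each, 70% reduction, two-sided 0.05, Wald test on the log ratio of mean infection rates, 1,500 runs, no adjustment for gametocyte density. Grouping by receipt gives, for assumed intra-child correlations of 0.1 / 0.2 / 0.4:

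- comparator infection rate 5%: 98% / 84% / 58%
- comparator infection rate 10%: >99% / 99% / 88%
- comparator infection rate 20%: about 100% throughout

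So >90% is plausible for the receipt contrast in most of these scenarios.

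**2. Attenuation under detectability grouping.** Let u be the share of the 100 recipients without detectable drug. Assume the 70% reduction holds in every recipient and that no non-recipient has detectable drug. Then:

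- comparator mean, relative to untreated = (100 + 100u × 0.3) / (100 + 100u)
- apparent reduction = 1 − 0.3 / (comparator mean)

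For u = 0.5 the comparator mean is 115/150 = 0.767, and 1 − 0.3/0.767 = 0.61. The last two columns repeat the simulation at an assumed 10% infection rate.

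| u | Exposed / comparator | Apparent reduction | Power, correlation 0.2 | Power, correlation 0.4 |
|---|---|---|---|---|
| 0 (same as receipt) | 100 / 100 | 70% | 99% | 88% |
| 10% | 90 / 110 | 68% | 97% | 83% |
| 25% | 75 / 125 | 65% | 93% | 69% |
| 50% | 50 / 150 | 61% | 71% | 42% |
| 75% | 25 / 175 | 57% | 44% | 36% |
| 90% | 10 / 190 | 55% | 38% | 31% |

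Power at u of 75% or more is rough, because few exposed children remain. The loss of power is larger than the attenuation.

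**3. How large might u be?** The SAP gives no detection limit, half-life or expected undetectable share. Section 7 expects a median DEAQ of 550 ng/mL (IQR 350-850) four days after the last directly observed dose. On the log scale the IQR is 5.86-6.75, so the SD is 0.89/1.349 = 0.66. Section 10.3 places that sample at day 7 of the round, so the first day of the next round is about 30 − 7 = 23 days later. With log-linear decline, median = 550 × 2^(−23/half-life), and u is the normal probability of lying below the detection limit. For assumed limits of 1 to 25 ng/mL:

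- half-life 7 days or more: u at most 11%
- half-life 5 days: u from 0% to 56%
- half-life 3 days or less: u from 7% to 100%

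The documents do not narrow this range. For feeds shortly after directly observed dosing, u should be small.

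**The case against.** The strongest defence is that the analysis matches the endpoint. Sections 5.3 and 10.7 define endpoint 12 as infectivity in relation to gametocyte density and AQ/DEAQ level, so a drug-level analysis is required. This stands: the receipt contrast should be added to that analysis and should not displace it.

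Second, timing. Besides first-day sampling, feeds are planned shortly after SMC, when receipt and detectability should nearly coincide in arm 3. This also stands, and it means the misclassification may be slight.

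Third, gametocytes present after the drug has waned need not be those that met it, so receipt grouping could itself dilute the effect. That is a fair reason to record time since last dose. It does not remove the mismatch with the stated hypothesis and power.

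Some stronger readings are tempting but unsupported:

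- *Receipt is never compared.* The conditional van Elteren test refers to arms, and arm is the receipt grouping of Section 7.
- *The effect would be hidden.* The untreated children remain in the comparator, so even at 90% undetectable a 70% reduction still appears as 55%.
- *A randomised contrast is being discarded.* Feeders are selected on gametocyte positivity after treatment began, so arm 3 versus arms 1 and 2 is not a clean randomised comparison either.
- *Drug from other sources in arms 1 and 2 argues for grouping by arm.* The SAP documents no such exposure, and grouping by arm would place such a child in the comparator.

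**Conclusion.** The mismatch is real. Section 7 poses and powers a question about SPAQ receipt; the two model-based analyses of endpoint 12 answer one about detectable drug. If sterilisation is permanent, recipients without detectable drug dilute the comparator: a true 70% reduction appears as about 68% with 10% undetectable, 61% with 50% and 55% with 90%. In the 10% infection-rate example, power falls seriously only when roughly half of recipients are undetectable, or about a quarter when between-child variation is high.

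These figures assume a uniform 70% effect in all recipients, and the power figures also depend on assumed infection rates and correlations. The undetectable share is not stated, so the actual loss is unknown and may be small. Endpoints 12 and 13 are exploratory and no primary or secondary result is affected. The case for changing the plan is that the correction is cheap and restores the comparison the experiment was sized for.

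**What to change.** In Section 10.7:

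1. **Endpoint 12.** Add, as the test of sterilisation, the contrast by prior SPAQ receipt: arm 3 versus arms 1 and 2, ages 5-9, at a given gametocyte density, with time since last dose recorded. Keep the detectability and concentration analyses alongside it, as the endpoint definition requires.
2. **Van Elteren test.** State that its groups are these same receipt groups.
3. **Endpoint 13.** Base the choice between one curve and arm-specific curves on the receipt effect rather than on drug detectability alone, and correct the cross-reference to item 8.

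The cost is SAP wording and one extra exploratory contrast. No new data are needed, since arm is known and arm 3 dosing is directly observed (Section 10.3). The report should say that the receipt comparison is not a clean randomised one, because feeders are selected on gametocyte positivity after treatment began.

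### Exploratory endpoint 13 uses a single density-infectivity curve unless the drug effect is statistically significant, but the feeding assays are powered only for a 70% reduction, so a non-significant result does not show equal infectivity

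*SAP*

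**What the plan says.** SAP section 10.7, endpoint 13, estimates the size and age distribution of the infectious reservoir from observed mosquito infections together with transmissibility imputed from gametocyte density. Two branches govern the imputation curve. The first opens "If drug levels do not influence infectivity (see 8), a" and goes on to one modelled curve for everyone. The second reads "If drug levels do have a statistically significant impact on transmission potential, all estimates of the infectious reservoir within one month of SMC" and makes those estimates depend on study arm. For the end-of-study survey, no drug effect on transmission is assumed in either branch.

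Section 7 gives the only power figure for the feeding assays. With 100 children who received SPAQ, 100 who did not, and "dissecting 40 mosquitoes per experiment", it states that "we would have >90% power to detect a 70% reduction in infectivity". It also warns that "the exact number of experiments that can be conducted will be dictated by mosquito husbandry". The same section says that comparing density-infectivity associations "can demonstrate whether imputation is indeed acceptable across populations", and gives sterilisation of gametocytes by SPAQ as the working hypothesis.

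**The concern.** Significance is the only criterion the SAP names for letting a drug effect into the reservoir estimate. It sets no equivalence margin, no confidence-interval criterion and no sensitivity analysis with separate curves. In practice, then, a non-significant test selects the single curve, which fixes the ratio of treated to untreated infectivity at a given density at exactly 1. That conclusion needs evidence of similarity. A test sized for a 70% reduction can be inconclusive when the true effect is moderate.

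At stake is objective iii, the reservoir under conventional versus extended SMC. Only arm 3 treats children aged 5-9 years. If the gate wrongly stays closed, any lower infectivity per gametocyte in those treated children is averaged away in the imputed part of the arm comparison within one month of SMC.

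**Working it through.** **Inputs from SAP section 7:** 100 versus 100 children, 40 mosquitoes each, power above 90% for a 70% reduction (ratio 0.30), median gametocyte density about 14 per µL with IQR 1.8 to 44.2. **Assumed:** a two-sided 0.05 test. The SAP states 0.05 for the primary sample size but no level for this test. Baseline infectivity and between-child variation are not given either, so the power figure cannot be reproduced exactly. It is attainable under plausible values (below).

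**1. Back-calculation from the stated power.** For a Wald test on the log ratio, SE = −ln(0.3) / (1.96 + z_power), with −ln(0.3) = 1.204.

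- Power 90%: 1.204 / (1.960 + 1.282) = 0.371
- Power 95%: 1.204 / (1.960 + 1.645) = 0.334
- Power 99%: 1.204 / (1.960 + 2.326) = 0.281

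Holding that SE constant, the miss rate for a reduction r is 1 − Φ(−ln(1 − r)/SE − 1.96). For r = 0.3 and SE = 0.371: 0.357/0.371 − 1.96 = −1.00, Φ = 0.159, miss rate 84%.

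| Power at 70% | Miss 30% | Miss 40% | Miss 50% |
|---|---|---|---|
| 90% | 84% | 72% | 54% |
| 95% | 81% | 67% | 45% |
| 99% | 76% | 56% | 31% |

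**2. Simulation.** The SE need not be constant across effect sizes, so the design was also simulated. Log density was normal with SD ln(44.2/1.8)/1.349 = 2.37, the logistic slope was 0.5 per log unit, variation between children was beta-binomial, and the test was a log-link model with robust SE. Infection rates at median density and the intraclass correlation (ICC) are assumptions.

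| Infection rate, ICC | Power at 30% | Power at 50% | Power at 70% |
|---|---|---|---|
| 10%, 0.2 | 59% | 96% | 100% |
| 5%, 0.1 | 56% | 95% | 100% |
| 5%, 0.2 | 35% | 74% | 98% |
| 2%, 0.1 | 25% | 63% | 91% |
| 2%, 0.2 | 19% | 42% | 71% |

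The last row conflicts with the stated power and is set aside. In the other four, a 50% reduction is missed about 4 to 37% of the time and a 30% reduction about 41 to 75%.

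A second simulation used a logit-scale random effect per child and mean infection rates of 2 to 20%. In the nine of its twelve settings where the density-adjusted regression test had at least 90% power at 70%, that test missed a 50% reduction 0 to 45% of the time and a 30% reduction 9 to 77%. The low ends come from a 20% infection rate with little variation between children.

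**3. Effect of a missed reduction.** With equal groups at like densities, the pooled curve sits at (1 + (1 − r))/2 = 1 − r/2 of untreated infectivity.

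- r = 0.3: 0.85. Treated overstated by 0.85/0.70 − 1 = 21%; untreated understated by 15%.
- r = 0.5: 0.75. Treated overstated by 0.75/0.50 − 1 = 50%; untreated understated by 25%.

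**4. Which test opens the gate.** The cross-reference to item 8 leads to gametocyte prevalence; infectivity by drug level is endpoint 12. Endpoint 12 lists several analyses and groups children by detectable drug, while the power statement groups them by SPAQ receipt. The 100:100 split, and its power, may not carry over.

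**The case against.** The best defence is that the plan expects a large effect. Under permanent sterilisation, a 70% target is reasonable, and nothing in the SAP calls a 30 to 50% reduction important. The stated power is also a lower bound. Both points stand, and they limit how often the gate would mislead. They do not make a non-significant result evidence of equal infectivity.

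A reader might infer several stronger things that the SAP does not support:

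- **That a 50% reduction would usually be missed.** The 54% figure needs power of exactly 90% and a constant SE. In favourable simulated settings compatible with section 7, the miss rate is 5% or less.
- **That the drug effect disappears from the report.** Endpoint 12 compares infectivity by drug detectability and by concentration whatever the p-value. Endpoint 13 also uses observed infections, and arm differences through gametocyte density remain.
- **That the planned interval is too narrow.** No interval method is stated for endpoint 13, so this cannot be shown.
- **That the whole reservoir analysis is affected.** The gate covers only estimates within one month of SMC. The week-5 survey falls outside that window, and the end-of-study estimate assumes no drug effect in any case.

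**Conclusion.** The point holds as a low-severity improvement to an exploratory analysis. As written, an inconclusive test forces equal infectivity at equal density in the imputed reservoir within one month of SMC, and the stated power does not justify that step. The concern is firmest for reductions of 30 to 40%: miss rates of 76 to 84% and 56 to 72% by back-calculation, if power at 70% is 90 to 99%. At 50% the answer depends on unstated inputs: 31 to 54% by back-calculation, and about 4 to 37% in the first set of simulated scenarios that fit section 7. All these rates assume a two-sided 0.05 test, and all are lower if baseline infectivity is high with little variation between children. The overstatement of treated infectivity by 21% (true 30% reduction) or 50% (true 50% reduction) assumes equal groups at like densities. No primary or secondary result depends on the gate.

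**What to change.** Remove the gate from endpoint 13. Fit one density-infectivity model with a drug-exposure term, and always carry its estimate and uncertainty into the within-one-month reservoir estimates, for example by bootstrapping children. Report the single-curve version as a sensitivity analysis. If the sponsor prefers the single curve as the main analysis, allow it only when the confidence interval for the infectivity ratio lies inside a margin stated in advance. Correct the cross-reference from item 8 to endpoint 12.

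The cost is a change of SAP wording and a few lines of code, with no new data. The downside is somewhat wider intervals if the true drug effect is nil.
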